Parturients will be included if they are delivering the first child and are planning to labor with neuraxial analgesia. Additionally, there will need to be sufficient time before delivery to allow the completion of the Pre procedure questionnaire, State-Trait Anxiety

Inventory (STAI) questionnaire both before and after the procedure, as well as the Newest Vital Sign questionnaire and the Pain Catastrophizing Scale questionnaire before the procedure. They will be included if they are ASA 2. Furthermore, they be required to read and comprehend the English language, as the Newest Vital Sign questionnaire requires them to read and interpret a nutrition label.

Physician Inclusion:

Anesthesiology Attending, Fellow or Resident Physicians who participants in the placement of the epidural catheter placement

Companion Inclusion:

Primary companion identified by parturient over the age of 18

Exclusion: Parturients will be excluded if they are receiving neuraxial anesthesia for a cesarean delivery, external cephalic version, or other non-labor procedure. They will also be excluded if they begin to push for delivery before completion of the STAI questionnaire following labor epidural catheter placement. They will be excluded if there is no support person present at the time of the neuraxial procedure. They will be excluded if they are ASA 3 or greater, or if they have a contraindication to receiving any of the medications routinely used in the placement of a labor epidural catheter (lidocaine, bupivacaine, epinephrine, fentanyl). Adults who are unable to consent and minors will be excluded.

STUDY-WIDE NUMBER OF PARTICIPANTS:

The total number of participants has been determined to be 75 per group, for a total of 150.

STUDY-WIDE RECRUITMENT METHODS:

Potential participants will be recruited while they are on the labor and delivery ward at Prentice Women's hospital, prior to the placement of a labor epidural catheter. They will be approached by a member of the research team.

Potential participants will be identified by interview and personal history, as well as by anesthesia and obstetric notes in the electronic medical record.

No advertisements will be used to recruit participants for the study.

MULTI-SITE RESEARCH:

N/A

STUDY TIMELINES:

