The duration of an individual's participation extends from initial enrollment while on the labor and delivery ward prior to labor epidural catheter placement until the completion of the STAI questionnaire and survey following this procedure. The duration of the study enrollment is anticipated to be 3-5 months, with the plan to enroll an average of 2-4

parturients daily, and accounting for study drop-outs. The estimated date for study completion is late spring to early summer of 2017.

STUDY ENDPOINTS:

The primary endpoint for the study is:

- Does having a support person present when it is the desire of the parturient has a positive effect on maternal satisfaction during the placement of epidural catheter for labor analgesia?

The secondary endpoints are:

- Does having a support person present when it is the desire of the parturient has a positive effect on maternal anxiety during the placement of epidural catheter for labor analgesia?
- Does having a support person present when it is the desire of the parturient have a positive effect on maternal perception of pain during the placement of epidural catheter for labor analgesia?
- Does the presence of a support person affect the perceived difficulty of the procedure by the provider placing the labor epidural catheter?
- Does the level of health literacy of a parturient affect her level of anxiety?
- Does the degree of Pain Catastrophizing affect the parturients level of anxiety?
- Does the relationship of the parturient to the support person have an effect on the level of anxiety of the parturient?
- Does the ethnicity of the parturient have an effect on the level of anxiety?
- Does induction of labor versus spontaneous labor have an effect on the level of anxiety of the parturient?

PROCEDURES INVOLVED:

Parturients who have been admitted to the Labor and Delivery ward at Prentice Women's Hospital will be approached by a member of the research team prior to the placement of a labor epidural catheter. They will be asked if they are considering neuraxial labor analgesia, and if they are they will be screened using the inclusion and exclusion criteria to determine study eligibility. Once they have been evaluated and found to be appropriate for the study, they will be invited to participate.

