Participants will be asked to fill out the STAI questionnaire to assess the level of anxiety prior to placement of the labor epidural catheter, and before knowing their group assignment. They will then complete the pre procedure questionnaire. This questionnaire asks about expectations she has for the labor epidural procedure. They will then be given the page of the Newest Vital Signs questionnaire with the Nutrition Facts, and be asked the 6 questions by the recruiter. Then they will be asked the Pain Catastrophizing Scale questionnaire with 13 statements, and asked to respond as directed by the instructions stated by the researcher. They will then be asked who their primary support person is. A form will be handed to that person to confidentially record if he/she would prefer to be present for the procedure. This form will be collected from the support person, and without the parturient aware of the support person's response, she will be asked for her preference with regard to the presence of a support person in

the room, which will be recorded on this form as well. Finally, she will be asked which ethnicity she most relates to, also to be recorded on this form.

After all these data have been collected, the parturient will be randomized as to whether her companion will be allowed in the room or will be asked to leave. This will not be communicated to the parturient until the time of the labor epidural catheter placement. When she requests the neuraxial labor analgesia, the provider placing the labor epidural catheter will be made aware of which group she has been randomized to, and will either ask the companion to leave for placement, or provide the companion a non-mobile chair to sit on in front of the parturient for placement of the labor epidural. The companion will be asked to remain in the chair. He/she will be asked to focus on the parturient. It will be emphasized that he/she must remain seated and will not be allowed to observe the procedure being performed. This is to prevent loss of consciousness in the companion, which has been documented in the literature (Devore and Asrani, 1978; Crosby and Halpern, 1989). One violation will result in a warning, and after a second the companion will be escorted out of the room and the participant will be removed from the study.

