The provider will place the labor epidural catheter in the regular fashion, as is common practice at Prentice Women's Hospital. After preparation and draping of the skin in the sitting position, infiltration with Lidocaine 1% will be conducted at L3-L4 or L4-L5. A 17g Tuohy needle will be advanced into the epidural space, using a loss of resistance with either saline or air, depending on the provider's preference. After the epidural space has been located, a 27g pencil-tip spinal needle will be placed through the Tuohy, into the intrathecal space, and an intrathecal dose of medication will be administered. The exact dose to be injected will be left up to the discretion of the provider, who will determine the appropriate dose based on the patient's situation at that time. After the intrathecal dose is administered, the spinal needle will be removed and a 19g epidural catheter will be placed through the Tuohy into the epidural space. It will be secured at the skin with a sterile dressing and tape, leaving 5cm of the catheter in the epidural space. The patient will then be placed in a lateral position.

After the completion of the neuraxial procedure, the study participant will be asked to record her overall satisfaction with the procedure, as well as her perception of pain during the placement of the labor epidural catheter, using two VAS from 0-100mm. Additionally, she will be asked to complete the STAI questionnaire again. Finally, she will be asked to complete the post procedural questionnaire. At that point the parturient's participation in the study will be complete.

The provider or research team member will be asked to fill out the Participant's Demographics Information form.

The provider placing the labor epidural catheter will be asked to evaluate his/her ability to palpate landmarks for placement, the positioning of the patient, and overall perceived difficulty with the epidural placement, using a VAS from 0-100mm for each, which will be kept confidential. Additionally, they will complete a short series of questions focusing on

the presence of a companion for the procedure. No identifying information from the provider will be recorded on this form.

DATA AND SPECIMEN BANKING:

N/A

DATA AND SPECIMEN MANAGEMENT:

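### A randomised woman who starts pushing before finishing the second STAI, a secondary-endpoint form, is excluded even if her primary satisfaction score is already recorded

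*Combined protocol and SAP*

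**What the plan says.** - **The rule.** Inclusion and Exclusion Criteria (Exclusion): "They will also be excluded if they begin to push for delivery before completion of the STAI questionnaire following labor epidural catheter placement".
- **A screening version of the same idea.** The Inclusion paragraph of that section already says that "there will need to be sufficient time before delivery to allow the completion of the Pre procedure questionnaire", and extends this to the other forms, including the STAI both before and after the procedure.
- **Randomisation.** Procedures Involved places it after the baseline forms and before catheter placement: "After all these data have been collected, the parturient will be randomized as to whether her companion will be allowed in the room".
- **Endpoints.** Under Study Endpoints, the primary question is whether a desired companion's presence "has a positive effect on maternal satisfaction during the placement of epidural catheter for labor analgesia". The first secondary question is whether it "has a positive effect on maternal anxiety during the placement of epidural catheter for labor analgesia".
- **Order of post-procedure forms.** In Procedures Involved the woman is first "asked to record her overall satisfaction with the procedure" and to rate pain, on two VAS. Then: "Additionally, she will be asked to complete the STAI questionnaire again". The post-procedure questionnaire comes last.
- **Retention of data.** Withdrawal of Participants keeps data collected before a withdrawal, but the stated purpose is to learn what predicts failure to follow instructions. No analysis set is defined anywhere.
- **Numbers.** Number of Local Participants plans for 150 completers (75 per arm), recruits 180, and expects few women to become ineligible.

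**The concern.** A criterion that can be checked only after the assigned procedure is a post-randomisation exclusion, wherever it is placed in the protocol. Here the trigger is an unfinished form for a secondary endpoint, yet the consequence, as worded, is removal from the trial as a whole. A woman could complete both VAS scales, begin pushing partway through the STAI, and leave the primary comparison although her primary outcome is on file. Her pre-procedure STAI, completed before randomisation, would go too.

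At stake is the comparison of the groups as randomised. Each such removal gives up usable data and makes inclusion depend on something that happens after assignment. By then the woman and the provider both know the arm, and the protocol sets no time limit for the post-procedure forms.

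**Working it through.** **1. The plan's own figure.** Data and Specimen Management states 81% power with 75 per arm for a mean difference of 4.7, two-sided alpha 0.05, Mann-Whitney-Wilcoxon test. It gives no SD, outcome or units, so the figure cannot be reproduced from stated inputs. Using power ≈ Φ(4.7 / (SD × √(2/n)) − 1.96):
- With n = 75, 81% power implies an SD of about 10.1: 4.7 / (10.14 × 0.1633) − 1.96 = 0.88, and Φ(0.88) = 0.81.
- With the Mann-Whitney efficiency for normal data, n = 75 × 3/π = 71.6, and the implied SD is about 9.9.

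The point does not depend on this. The 4.7 serves only as a yardstick in step 4.

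**2. Sequence of events.** Setting Procedures Involved beside the exclusion rule:

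| Step | Event | Endpoint served |
|---|---|---|
| 1 | Baseline STAI and other forms | Baseline |
| 2 | Randomisation | – |
| 3 | Arm disclosed, catheter placed | – |
| 4 | Satisfaction VAS and pain VAS | Primary; secondary |
| 5 | Second STAI | Secondary |
| 6 | Post-procedure questionnaire | – |

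For a randomised woman whose catheter has been placed, the rule applies if pushing starts at any time before step 5 is finished. If pushing starts before step 4, there may be no VAS to lose. If it starts between the end of step 4 and the end of step 5, a recorded primary outcome is excluded.

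**3. How many women.** The protocol gives no rate. The 1% to 5% range is an assumption, applied to 180 as though every recruit were randomised:
- 180 × 0.01 = 1.8, about 2 women
- 180 × 0.05 = 9 women

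These are the women who trigger the rule. Those who lose a recorded VAS are a subset whose size cannot be estimated from the protocol. Even at the upper figure, 180 − 9 = 171, above the 150 required, so this rule alone does not threaten the sample size.

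**4. How large a bias could be.** Suppose a share e of an arm is excluded, and those women average g mm below the mean of all women randomised to that arm. The mean of the women kept is then too high by e × g / (1 − e), and the shift in the treatment difference is the gap between the two arms' values. Both e and g are assumptions.

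| e in one arm | g (mm) | Shift if the other arm loses e/2 | Shift if the other arm loses none |
|---|---|---|---|
| 1% | 5 | 0.03 | 0.05 |
| 5% | 10 | 0.27 | 0.53 |
| 5% | 20 | 0.54 | 1.05 |
| 10% | 20 | 1.17 | 2.22 |

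Check of the last row: 0.10 × 20 / 0.90 = 2.22; 0.05 × 20 / 0.95 = 1.05; 2.22 − 1.05 = 1.17. With equal e and equal g in both arms the shift is 0. Comparing these shifts with 4.7 further assumes that 4.7 refers to the satisfaction VAS in mm, which the protocol does not say.

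**The case against.** The strongest reply is that no bias is shown. The arms differ only in whether a companion sits in the room during placement, assignment is withheld until then, and nothing in the protocol suggests that this changes when pushing begins. Every non-zero shift in the table comes from assuming unequal exclusion. This stands. A reader might infer that the rule distorts the primary comparison; the documents do not support that.

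A reader might also infer that the rule removes the fastest labors and so undermines the secondary question "Does induction of labor versus spontaneous labor have an effect on the level of anxiety of the parturient". That does not follow. The rule selects on the interval from placement to pushing: a long labor with a late request for analgesia can trigger it, and a quick labor with early placement may not. Nor would keeping these women restore their post-procedure anxiety scores. Only the baseline STAI is recovered.

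The numbers are likely to be low: first births only, a screening judgement about time, and a stated expectation of few ineligible women. That also stands.

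Finally, the text is looser than a strict reading implies. The order of VAS before STAI comes from the sequence in which they are listed, not from a timing rule. That the satisfaction VAS is the primary measure comes from joining two sections. No sentence says outright that an excluded woman's VAS is discarded. However, the exclusion is unqualified, the target is counted in completers, and no analysis set brings her back.

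Two replies carry less weight. Recruiting 180 restores numbers but not the women removed, and that allowance is described in terms of voluntary drop-out and protocol violation. The screening judgement already covers time for the forms, so for a woman already randomised the exclusion adds only her later removal.

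**Conclusion.** The point holds as a design fault that is cheap to correct. As written, the rule is a post-randomisation exclusion, triggered by a secondary-endpoint form, that can discard an available primary outcome and a pre-randomisation STAI. Under an assumed 1% to 5% of 180, 2 to 9 women would trigger it, and fewer would lose primary data. It would be wrong to read 2 to 9 as the number of primary outcomes lost.

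Differential loss between arms is possible but not demonstrated. Under the assumptions above, the shift runs from zero with balanced loss to about 1 mm when 5% are lost from one arm only with a 20 mm gap, and to about 2.2 mm at 10%. The conclusion rests on three readings: that exclusion means removal from the primary analysis, that the forms are completed in the order listed, and that the satisfaction VAS is the primary measure.

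**What to change.** 1. Delete the post-procedure exclusion. Apply the time criterion only before randomisation, which the inclusion criterion already does.
2. Add a statement of this kind: *The primary analysis includes every randomised woman with a satisfaction VAS, in her assigned arm, whether or not the second STAI was finished. Any post-procedure form not completed, VAS or STAI, is treated as missing for that endpoint only. The baseline STAI is kept. The number of such cases is reported by arm.*

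This wording also covers a woman who pushes before completing the VAS: her primary outcome is missing and is reported as such. The withdrawal rule for companion conduct is a separate post-randomisation removal, not assessed here, and should be checked for consistency with the new statement.

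The cost is a short text change, with no added participants or procedures. The downside is a few missing STAI values to report.

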- The member of the anesthesia team recruiting the participants will be educated in the use of the STAI, pre and post procedure, Newest Vital Sign, and Pain Catastrophizing questionnaires prior to enrolling participants. The primary recruitment will be by the anesthesia research nursing staff that has extensive experience in recruiting participants to various studies.
- We expect to recruit 2-4 participants on a daily basis, as the number of labor epidural catheters placed during a given 24 hour period well exceeds 20. By recruiting 1 participant every day (<5% of laboring parturients each day), or 7 in a week period, the data collection would take 22 weeks, which is within the proposed 3-5 month recruitment period.
- This research will be conducted primarily by [name]. and [name]. the latter of which is the current Fellow in Obstetrical Anesthesiology and has 3 months of devoted time during this fellowship year for research.
- While the collection of data will occur in the Labor Suite on the Labor and delivery ward, the analysis of these data collected during the study will be analyzed in the Office of Obstetrical Anesthesiology 9th floor Prentice as well as in the main Anesthesiology Office in Arkes 10th floor. These locations are restricted to personnel in the Department of Anesthesiology and are not located in patient care areas.
- Participants will have access to the members of both the research and anesthesia teams on call, before and after placement of the labor epidural catheter, who can answer any questions they may have regarding the procedure.
- Prior to recruiting participants, the study protocol will be reviewed by the anesthesia research study team.
- The provider placing the labor epidural catheter will be informed of which group the parturient was randomized into just before entering the room for the procedure. At that time they will either ask the companion to leave the room or ensure that there is a non-mobile seat for the companion in front of the parturient.

PRIOR APPROVALS:

Department of Anesthesiology Research Committee

RECRUITMENT METHODS:

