Participants will be recruited on the Labor and Delivery Ward 8th floor of Prentice Women's Hospital. They will be approached regarding participation if they meet inclusion criteria during chart review or initial pre-anesthesia interview. Both patients in spontaneous labor and those scheduled for induction of labor will be approached if they meet criteria. The GE Centricity computerized board that lists all active laboring parturients is available in the anesthesia work room for review of the current Labor and Delivery census. If the patient is nulliparous she will be approached by a member of the

research team with regard to enrollment in the study. No reimbursement will be offered for participation.

NUMBER OF LOCAL PARTICIPANTS:

A total of 150 participants will complete the study. Half of the participants (n=75) will be randomized to the “companion in the room” group and half (n=75) will be randomized to the “companion out of the room” group. We are anticipating minimal patients who enroll to become ineligible during the study, since the total duration of enrollment is likely less than a couple hours, however we will attempt to recruit 180 participants in total to allow for a 20% drop-out rate, either by choice or by protocol violation.

Resident Participation: A total of 64 participants

Attending Physician: A total of 30 participants

Companion: A total of 150 participants

CONFIDENTIALITY:

Data will be stored in a department server which is password protected. Each study subject will be assigned a study code number. The code will be used to link study data to patient identification (name) in a separate database. Subject data will be stored on secured password protected computers at Northwestern University and Department of Anesthesiology servers. Paper data will be completed by research study team members and will be entered into REDCap. The paper folders will be stored in Arkes Pavilion 10th floor Department of Anesthesiology administrative office via key card controlled front door and key controlled closet. Data access will be password protected and only available to study investigators via REDCap. REDCap access will be controlled by the Principal Investigator. Data both electronic and paper will be destroyed 5 years after manuscript preparation.

PROVISIONS TO PROTECT THE PRIVACY INTERESTS OF PARTICIPANTS:

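### The exclusion for having no support person is judged at the procedure, after randomisation and with the group known to the provider, so it can be applied differently in the two arms

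*Combined protocol and SAP*

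**What the plan says.** The Exclusion paragraph of INCLUSION AND EXCLUSION CRITERIA states: "They will be excluded if there is no support person present at the time of the neuraxial procedure". It does not say whether presence is judged before or after the assignment is acted on, or by whom.

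PROCEDURES INVOLVED puts randomisation earlier, straight after the questionnaires and the preference form: "After all these data have been collected, the parturient will be randomized as to whether her companion will be allowed in the room". Of the assignment it adds: "This will not be communicated to the parturient until the time of the labor epidural catheter placement". The provider learns it at a later event: "When she requests the neuraxial labor analgesia, the provider placing the labor epidural catheter will be made aware of which group" she is in. The provider then "will either ask the companion to leave for placement, or provide the companion a non-mobile chair". RESOURCES AVAILABLE places this disclosure at the door: the provider "will be informed of which group the parturient was randomized into just before entering the room for the procedure".

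NUMBER OF LOCAL PARTICIPANTS plans 150 completers, 75 per group, from 180 recruited. No section defines an analysis population that keeps all randomised women in their assigned group.

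**The concern.** An eligibility rule is harmless to a randomised comparison if it is settled before assignment, or afterwards by someone who cannot know the assignment. Here neither is assured. The rule also concerns companion presence, which is the thing the two arms are meant to differ on. Selective removal on that factor would leave two groups that are no longer comparable by design, and the primary endpoint, maternal satisfaction, would carry the difference. The most plausible direction, if women without a companion at hand are less satisfied for other reasons, is in favour of companion presence.

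**Working it through.** The protocol has no figure of its own on this point to reproduce. Its 81% power statement does not bear on the order of events. The check is to set the sections side by side.

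**Order of events**

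1. Consent, baseline forms, companion's and woman's preferences (PROCEDURES INVOLVED).
2. Randomisation (same section).
3. Request for analgesia; provider told the group at the request or just before entering the room (PROCEDURES INVOLVED; RESOURCES AVAILABLE).
4. Companion asked to leave or given a seat; procedure performed.
5. The support-person exclusion refers to the time of the procedure, so it falls at step 3 or 4, after step 2.

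**Who knows the group then.** The woman does not know it until placement. The provider does. No step confirms that a companion is on hand before the provider is told.

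**What a missing companion means in each arm**

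| Arm | Assigned action | If no companion is there |
|---|---|---|
| Companion in | Companion seated in front of the woman | Assignment cannot be delivered; exclusion is the natural result |
| Companion out | Companion asked to leave | The procedure goes ahead just as assigned; nothing forces an exclusion |

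A companion who steps out once the assignment is known raises the same asymmetry: it defeats the companion-in assignment and matches the companion-out one.

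**What a bias would depend on.** Let *f* be the share of women with no companion at the procedure, *L* their mean shortfall in satisfaction against other women in the same arm, and *q* the share of them excluded in the companion-out arm. Suppose all of them are excluded in the companion-in arm. The share of such women left in the companion-out arm is

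r = f(1 − q) / [1 − f + f(1 − q)], and bias = L × r.

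- q = 1 (equal application): r = 0, so bias = 0.
- q = 0 (never applied in companion-out): r = f, so bias = f × L.

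The documents give none of *f*, *L* or *q*. As an illustration only, assume f = 0.05 to 0.10 and L = 5 to 15 mm on the 0–100 mm scale:

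- q = 0: 0.05 × 5 = 0.25 mm, up to 0.10 × 15 = 1.5 mm.
- q = 0.5: (0.025/0.975) × 5 = 0.13 mm, up to (0.05/0.95) × 15 = 0.79 mm.

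These results show how the quantities combine; they do not estimate anything in this trial. They should not be expressed as a share of the planned 4.7 difference, because the sample-size statement in DATA AND SPECIMEN MANAGEMENT names neither the endpoint nor the unit of that figure.

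**The case against.** The strongest reply is that absence itself should be balanced. The assignment is withheld from the woman until placement and from the provider until the request or the door, so on the stated procedures nothing makes a companion more likely to be away in one arm before disclosure. That stands. It confines the risk to how presence is judged and acted on after disclosure.

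Second, a provider told to send a companion out would usually notice that nobody is there, and providers also answer questions about the companion afterwards. This also stands, and it makes large differences in enforcement unlikely. But noticing is not the same as excluding, and nothing obliges the provider to report an absence that fits the assignment. Nor does the protocol say who applies the rule; it may be research staff rather than the provider.

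Third, any shortfall in satisfaction would have to come from other features of these women, since every correctly treated companion-out woman has the procedure without a companion. That is fair, and is a further reason not to put weight on the illustrative figures.

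A reader might infer three stronger things that the documents do not support:

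- *That there is a long gap between randomisation and procedure.* The interval is not given, and the only indication is that "the total duration of enrollment is likely less than a couple hours". The point needs only the order of events.
- *That the rule excludes every correctly treated companion-out woman*, since her companion has left. The bare words allow this, but 75 companion-out completers are planned and the provider is to ask a companion who is there to leave. In context, present must mean on hand beforehand. The wording needs clarifying; the design is not void.
- *That women who never ask for an epidural bias the comparison.* They are lost before disclosure, so their loss should not depend on arm. It costs numbers, for which recruitment to 180 makes some allowance.

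**Conclusion.** The point holds as a matter of sequence. A post-randomisation exclusion, on the factor that the arms determine, is applied when the provider knows the group, with no as-randomised analysis to absorb unequal application. It does not show that the trial will be biased. The bias is zero under equal application and probably small otherwise, and its size cannot be found from the documents because the absence rate, the outcome difference and the enforcement gap are all unstated. It is worth correcting because the assignment is not used until the request, so the documents show no benefit from fixing it earlier.

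**What to change.** Keep consent and all baseline forms where they are. At the epidural request, have staff confirm in every case that a support person is available, and randomise only then. At minimum, keep the assignment closed to everyone involved, for example in a sealed envelope, until that check is recorded.

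Reword the criterion along these lines: no support person available at the epidural request, assessed before the assignment is opened. Do not use it as an exclusion afterwards. State that all women randomised after the check (or, under the minimum version, all whose assignment was opened) are analysed in their assigned group, and report by arm any companion found absent later.

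Randomising at the request also avoids randomising women who never ask for an epidural.

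The cost is a change of wording plus one operational demand: the assignment must be accessible at any hour, on a unit that RESOURCES AVAILABLE says places well over 20 labor epidural catheters in 24 hours. If that is hard to arrange, the sealed-envelope version closes the same gap without moving randomisation. Neither version deals with the other removals after randomisation, namely pushing before the second anxiety questionnaire and withdrawal for companion violations; those need their own analysis rule.
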